2.4.12 Data analysis (aim #1, #2 and #3)

Neuromuscular function The peak-to-peak amplitude of the M and V waves will be computed offline from unrectified EMG epochs. Although H waves will be normalized to the corresponding M_{max} , V waves will be normalized to the supramaximal M wave (M_{sup}) elicited concomitantly with the V wave (V/M_{sup}) (52). V waves with concomitant $M_{sup} < 90\%$ of the highest M_{sup} will be excluded from further analyses to ensure stable conditions (73). A general squares model will be fitted to the ascending part of the H-reflex recruitment curve and the following parameters will be then extracted (80): (a) current intensity at H-reflex threshold, (b) current intensity at 50% of H_{max} , (c) current intensity at H_{max} and (d) slope of the ascending limb of the recruitment curve at 50% of H_{max} . Data analysis will be computed exclusively for recruitment curves with r square values >0.90 (80). The amplitude of background surface EMG will be derived from the

average rectified value (ARV) analyzed over an epoch of 500 ms before stimulation. The ARV values will be normalized to those obtained during the highest MVC (ARV computed from a 500-ms time period centered at peak force) and expressed as a percentage. During the MVCs performed with supramaximal stimulation, EMG ARV will be computed using a 500-ms period before stimulation. Then, these values will be normalized to the corresponding M wave obtained during supramaximal stimulation (52). Analyses of twitch contractions will be based on the average of the 3 supramaximal measurements. We will determine maximal twitch torque amplitude, time to peak twitch torque and half-relaxation time (74). Volitional and evoked RTD will be measured in several time windows (0-50ms, 50-100ms and 100-150ms) from force onset, using the trial with the highest peak RTD value (74).

Heart rate variability (aim #2 and #3) Power spectral analysis will be performed based on autoregressive modeling, following data detrending and re-sampling (4Hz) (Kubios HRV Analysis Software for Windows, University of Kuopio, Finland). Two main components will be considered: low frequency (LF) – frequency band from 0.04 to 0.15 Hz; high frequency (HF) – frequency band from 0.15 to 0.4 Hz. The ratio LF/HF will be calculated as an index of sympathovagal balance (79).

2.4.13 Statistical analysis (aim #1, #2 and #3)

Normality will be verified through the Shapiro-Wilk test. Univariate ANOVAs will be used to explore differences in the impact of blood-flow occlusion vs. non-blood flow occlusion on each H-reflex and V-wave variable (aim #1). Repeated measures ANOVA will be computed to determine significant main effects for time (pre- vs. post-acute exercise), condition (resistance vs. supramaximal vs. endurance exercise) and time-by-condition interactions on pain tolerance/threshold/ratings, AP, HRV and H-

reflex parameters and V-wave amplitude with metaboreflex activation (aim #2). Repeated measures ANOVA will be computed to determine significant main effects for time (pre- vs. post training), condition (resistance vs. supramaximal vs. endurance training) and time-by-condition interactions on exercise performance, pain tolerance/threshold/ratings, AP, HRV, H-reflex parameters and V-wave amplitude with metaboreflex activation, and neuromuscular adaptations to training (aim #3). Correlations between the impact of exercise or training on pain tolerance/threshold/ratings and performance on H-reflex, V-wave, AP and HRV variables will also be explored. Significance level will be set at $p < 0.05$. All data will be treated using SPSS 25.0 for statistical analysis.

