2.2.2 Study design

In a randomized and crossover trial, on 2 different days, participants will be tested before and after performing acute bouts of different exercise modalities or

passive rest. Participants will be tested for: (1) pressure pain threshold, (2) cold pain tolerance with concomitant measures of AP and HRV, (3) the influence of metaboreflex activation (maintained submaximal isometric contraction followed by blood flow occlusion) on H-reflex and V-wave excitability. For those enrolled in endurance and resistance exercise modalities, participants will visit the laboratory on a previous day for $VO_{2\text{max}}$ and maximal repetition assessments for rigorous exercise prescription on experimental day. The experimental design is illustrated in figure 2.

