2.4.6 V wave recordings, contractile properties and octet contractions (aim #3)

Before and after long-term training, V waves will be recorded during 5 MVCs, with 1

min of rest between trials, via supramaximal electrical stimulation (150% of the current needed to evoke maximal M wave; 1-ms single square pulse) delivered to the tibial nerve when torque exceeds 90% MVC (52). Contractile muscular properties will be measured from muscle twitches evoked by three single pulses (1-ms square pulse) at 120% of the current needed to evoke maximal M-wave, delivered every 12s (74). Evoked octet contractions (8 pulses at 300Hz), which has been found to elicit the maximum capacity of rate of torque development, will be applied through three supramaximal pulses (at 120% of the current needed to evoke maximal M-wave), delivered every 12s (74).

2.4.7 H-recruitment curves and V-wave recordings with metaboreflex activation (aim #1, #2 and #3)

During the blood-flow occlusion trials, to ensure metabolite accumulation participants will previously perform a plantar-flexion contraction during 3 minutes at 40% MVC (aim #1). 25% MVC will be used in aim #2 and #3, in order to avoid any potential hypoalgesic effect to interfere with the analgesic effect of exercise or training protocols. There is evidence that 25% MVC isometric contraction for 5 min doesn't produce elevations in pain threshold (29) at the same time it is a contraction with sufficient intensity to produce nociceptive afferents activation (64). Then, using a rapid inflator system (Hokanson E20 AG101, Bellevue, WA), an adult-size cuff 12 x 124 cm (Hokanson, SC12L, Bellevue, USA) (placed on the upper portion of the thigh) will be inflated to a pressure of 300 mmHg to ensure complete blood-flow occlusion (75). This procedure will preserve the activation of group III/IV afferent fibers for subsequent measurement of H-reflex and V-wave excitability. To construct the H-recruitment curves, the upper current intensity (compatible with maximal M-wave) will be divided

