into 22 segments equally separated on a logarithmic scale, with 4 stimuli/intensity, to limit the time under ischemia (~4 min), randomly applied to construct the recruitment curves, delivered at 3s intervals. After 2 min rest, the isometric plantar flexion contraction will be repeated with subsequent thigh circulatory occlusion. V waves will be ~~delivered~~ during 5 MVCs with 15 s of rest between trials (63) to limit the time under ischemia (~2 min), via supramaximal electrical stimulation (150% of the current needed to evoke maximal M wave; 1-ms single square pulse) delivered to the tibial nerve when torque exceeds 90% MVC. In control condition of aim #1 this H-reflex and V-wave collecting procedure will also be used but without sustained isometric contraction followed by blood flow occlusion. In aim #2 it will be assessed 15-30 min post-exercise or rest.

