2.4.8 Pressure pain threshold (aim #2 and #3)

Pressure pain threshold (PPT) will be assessed on the right rectus femoris (exercising muscle) and biceps brachii (non-exercising muscle). We will use a handheld algometer to perpendicularly deliver pressures to the participants' skin, and the pressure force will be increased at a rate of approximately $1 \text{ kg}\cdot\text{s}^{-1}$. The pressure will be stopped when they feel the pressure became painful. This procedure will be repeated three times for each test site. To minimize the impacts of repeated stimuli on the experimental outcomes, a recovery period of 20–30 s will be set between each measurement. The pain

pressure threshold will be recorded as the average of these three measures (34). In aim #2 it will be assessed 0-15 min post-exercise or rest.

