2.4.9 Cold pain tolerance (aim #2 and #3)

A cold pain tolerance (CPT) test, with the participants comfortably seated while immersing the right foot into a tank 5cm above the ankle joint (13) in cold water at $\sim 2^{\circ}\text{C}$ ($1^{\circ} - 4^{\circ}$) (77) will be used to determine participants pain tolerance before and after both acute exercise and long-term training. Water temperature will be adjusted through immersion of ice until achieving the desired temperature. Participants will be instructed to remove their foot from the water at any time when unable to support strong cold nociception sensation. In aim #2 it will be assessed 0-15 min post-exercise or rest (after pressure pain threshold assessment). Once breathing frequency might modify the subjective level of cold pressor pain (77), we will fix ventilatory frequency using a metronome for standardize the duration of the inspiration and expiration phases (2s each).

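### Aim 2's planned ANOVA omits the passive-rest session, so its time effect cannot be attributed to exercise; the modality hypotheses of aims 2 and 3 also lack named comparisons with endurance

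*Combined protocol and SAP*

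**What the plan says.** **Design.** Section 2.2.1 allocates 24 participants at random, eight to each modality. Section 2.2.2 sets the schedule: "In a randomized and crossover trial, on 2 different days". It goes on to say that "participants will be tested before and after performing acute bouts of different exercise modalities or", the alternative being passive rest. Read together, modality is a between-participant factor and exercise versus rest is a within-participant factor.

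**Data collected.** Post-rest measurement is planned for each main outcome:
- H-reflex and V-wave (section 2.4.7): "In aim #2 it will be assessed 15-30 min post-exercise or rest".
- Pressure pain threshold (section 2.4.8): "In aim #2 it will be assessed 0-15 min post-exercise or rest".
- Cold pain tolerance (section 2.4.9): "In aim #2 it will be assessed 0-15 min post-exercise or rest (after pressure pain threshold assessment").

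**Analysis.** For aim 2, section 2.4.13 gives a repeated measures ANOVA with "time (pre- vs. post-acute exercise), condition (resistance vs. supramaximal vs. endurance exercise) and time-by-condition interactions". Aim 3 has the same structure, before and after training. Neither the ANOVA nor the planned correlations mention rest. No follow-up comparison and no error rule are given.

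**Hypotheses.** Section 1.3 allows that every modality could lower pain sensitivity after exercise. It then hypothesises that resistance and supramaximal exercise do so more than endurance, both acutely (aim 2) and after training (aim 3).

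**The concern.** A pre-to-post change on the exercise day has two parts: the effect of exercise, and whatever happens when the same painful tests are repeated within one session. The rest day exists to measure the second part. A model without it can identify an exercise effect only by assuming that retest change is zero.

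The protocol does not make that assumption elsewhere. Section 2.4.7 lowers the test contraction to 25% MVC "in order to avoid any potential hypoalgesic effect to interfere with the analgesic effect of exercise or training protocols", and section 2.4.8 spaces the pressure stimuli "To minimize the impacts of repeated stimuli on the experimental outcomes". These steps reduce test-induced change; only the rest session shows how much remains. Section 1.1 also reports that, in the evoked-potential study later used to size aim 2, the fall in laser-evoked potentials after exercise did not differ from passive rest. An analysis without a rest term could not have shown that.

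At stake is the claim that acute exercise produces hypoalgesia. A smaller matter is the modality hypothesis. The interaction test has 2 degrees of freedom, so it can say that changes differ, but not which modality differs from endurance or in which direction.

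**Working it through.** **Inputs from the documents:** 24 participants in three groups of 8; significance level 0.05. **Assumed, because the documents give no values:** retest drift, effect sizes and between-session correlation r. All effects are in units of the SD of the pre-to-post change. The plan's own figure of 24 for 80% power cannot be reproduced, because section 2.2.1 gives no effect size, SD, correlation or target test.

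**1. Planned time effect.** Error df = 24 − 3 = 21, two-sided critical t = 2.080, non-centrality = (effect + drift) × √24.

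| True effect | Drift | Non-centrality | Significant |
|---|---|---|---|
| 0 | 0.2 | 0.98 | 15% |
| 0 | 0.3 | 1.47 | 29% |
| 0 | 0.5 | 2.45 | 65% |
| 0.6 | 0 | 2.94 | 80% |
| 0.6 | −0.2 | 1.96 | 46% |
| 0.6 | −0.3 | 1.47 | 29% |
| 0.6 | −0.5 | 0.49 | 8% |

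An effect of 0.3 with no drift, no effect with a drift of 0.3, and an effect of 0.6 with a drift of −0.3 all have non-centrality 1.47. The time test cannot tell them apart.

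**2. Session-by-time instead.** Take each participant's exercise change minus rest change and regress it on modality and session order (df 20). Simulation used 8,000 runs per setting, r = 0.3 and order balanced 4/4 within modality. With no exercise effect it rejected 4.6% to 5.3% of the time for drifts of 0 to 0.5, with or without a 0.3 SD day effect. Power for an effect of 0.6 was 66% with no drift and 65% with a drift of −0.3.

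**3. Modality interaction.** In the same no-effect runs the planned time-by-modality test rejected 4.7% to 5.3% of the time. Drift common to randomised groups cancels.

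**4. Price in precision.** The SD of exercise change minus rest change is √(2(1 − r)). The differences detectable with 80% power (df 20) are:

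| r | SD of difference | All 24 | One modality (n = 8, pooled error) |
|---|---|---|---|
| 0 | 1.41 | 0.85 | 1.47 |
| 0.3 | 1.18 | 0.71 | 1.23 |
| 0.5 | 1.00 | 0.60 | 1.04 |
| 0.7 | 0.77 | 0.47 | 0.81 |

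The unadjusted time effect has 0.60.

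**5. Comparisons with endurance, 8 per group.** If resistance and supramaximal both differ from endurance by d, the interaction's non-centrality is 8 × (2/3)d². That is 3.41 at d = 0.8 and 7.68 at d = 1.2. On F(2, 21), power is 32% and 63%. The sign of d drops out, so the result is the same if endurance exceeds both. In 200,000 simulated trials per setting:

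| | Pairwise after significant interaction (d = 0.8 / 1.2) | Holm (d = 0.8 / 1.2) |
|---|---|---|
| Both exceed endurance, both found | 18% / 47% | 18% / 46% |
| Only one exceeds endurance, found | 25% / 55% | 23% / 51% |
| Familywise error under the null | 4.2% | 4.5% |

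**The case against.** **The formal hypothesis is untouched.** Aim 2's explicit hypothesis compares modalities, and the remark that all of them could reduce pain is only a concession. This is partly right: the modality interaction is a valid randomised comparison. But section 1.3 also sets out to examine the acute impact of exercise on nociception, and the time effect is the only planned test of that.

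**The size is unknown.** The rates follow from chosen drifts, and the protocol takes steps to limit test-induced change. This stands: the figures illustrate sensitivity and are not this trial's error rate. The confounding itself does not depend on them. The simulation's balanced session order is also an assumption, but session-by-time stays near 5% without it.

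**The remedy costs power.** At r = 0.3, power for an effect of 0.6 falls from 80% to 66%; at r = 0 it is 51%. That is true, but the higher figure belongs to a test that does not isolate exercise.

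**Follow-up tests are routine.** Endurance is a level of the condition factor, and group means will show direction. The second point is therefore missing detail, not a wrong analysis, and is rightly secondary. A single contrast of the average of the two modalities against endurance would have more power if both exceed it (42% and 75% at 0.8 and 1.2 SD), but it does not show that each one does.

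**Conclusion.** The concern holds. As written, aim 2 collects a within-participant control and does not analyse it, so a significant time effect cannot be credited to exercise and a null one cannot be read as no effect. With assumed drifts of 0.2 to 0.5 SD of change, the false-positive rate would be 15% to 65%. Equal drift in the opposite direction would cut 80% power to between 46% and 8%. Figure 2 is not available, but it illustrates the design; the analysis text lists its own terms.

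The finding is limited to aim 2's time effect and the pre-to-post change within each modality. The modality interaction stands. For aims 2 and 3, a significant interaction alone does not answer the directed hypothesis, because the comparisons with endurance are not named. This should be corrected before analysis.

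**What to change.** Amend section 2.4.13 as follows.

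1. **Aim 2, hypoalgesia.** Add session (exercise or rest) as a second within-participant factor, with session order as a between-participant factor to adjust for day. Equivalently, analyse exercise change minus rest change, adjusted for day. Base the claim on session-by-time, overall and with an estimate and confidence interval for each modality, and not on the time main effect.
2. **Aims 2 and 3, modality.** Keep time-by-condition (exercise session in aim 2). Name resistance versus endurance and supramaximal versus endurance as the comparisons that answer the hypothesis. Fix one error rule in advance: pairwise tests only after a significant interaction, which suffices for three groups, or Holm. Either controls error within one outcome, not across the many outcomes listed. Treat session-by-time-by-modality as descriptive, so that aim 2 has one test of modality.
3. **Power statement.** Do not attach the 80% in section 2.2.1 to the modality comparison unless its effect size and test are shown.

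The change is to wording only: no new data or participants, and the same software. The statistical price is the precision loss shown above when r is below 0.5. With eight participants per modality, the by-modality results will serve mainly as estimates.

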However, Ellingson et al. 2014 (36) showed that CPM is only a minor contributor to EIH due to differences in temporal and spatial manifestations. In fact, a significant CPM effect was observed only during evoked pain procedures (i.e. pressure), whereas EIH occurred following exercise. Also, during CPM a significantly larger effect on pressure thresholds was found at the remote sites compared to local sites, whereas EIH was significantly larger in the exercising body part compared to remote sites (13). Therefore, local and segmental mechanisms appear to play important roles for EIH.

Thus, the influence of exercise on reducing peripheral nociceptive sensitivity has also been explored as a mechanism of EIH (18). Preliminary data has provided indirect evidence that the hypoalgesic effect induced by exercise could be possible related to the modulation of the signal transmission via A-delta and C fibers. Using electroencephalographic evoked potentials, Jones et al. (2016) (11) verify that somatosensory-evoked potentials (SEPs) to noxious electrical stimuli delivered to the index finger were unchanged after elbow flexion isometric exercise at 40% MVC for 3 min, whereas laser-evoked potentials (LEPs) to noxious heat delivered to hand dorsum decreased after exercise. This result suggests that the peripheral nociceptor might be involved in EIH in humans, because laser heat stimuli activate peripheral afferents and electrical stimuli bypass the receptors by activating the axons of the nociceptive afferents (11). This was further corroborated by Jones et al. (2017) (37) where by blocking blood flow to an unexercised limb during cycling exercise, resulting in unchanged pressure pain threshold afterwards, provided evidence that factors that are released into the blood during exercise (opioids, cannabinoids, catecholamines), which interact with specific receptors, are able to inhibit the nociceptive signal and therefore modify input before reaching the central nervous system. Nevertheless, the effect of acute exercise on LEPs amplitude attenuation observed by Jones et al., (2016) (11) was not statistical different from the passive rest control condition. The approximately 230ms onset latency of LEP was only compatible with conductive velocity of fast myelinated A delta fibers. The augmented pressure pain threshold verified after exercise resulted from an assessment obtained over a period of

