seconds eliciting a sensation of gradually increasing pain, only compatible with the activity of non-myelinated C fibers, which were not directly measured by EEG. Thus, if exercise has greater effects on C compared to A delta fibers further investigation should be addressed on the desensitization role of both afferent fibers post exercise.

On the other hand, the effects of long-term training on nociception have been poorly investigated (18). To our knowledge, only three studies examined nociceptive modulation after exercise training in healthy individuals. Jones et al. (2014) (38) observed increases in ischemic pain tolerance in non-exercising region (upper limb), but not in pain threshold, after cycling training for 30 minutes at 75% of $VO_{2\text{max}}$ 3 times/week for 6 weeks. Recently, in an attempt to establish intensity-dependent effects, O’Leary et al. (2017) (39) observed that 3 times/week for 6 weeks of high intensity cycling interval training but not volume-matched moderate intensity continuous training increased ischemic pain tolerance in the upper limb. On the opposite, Hakansson et al. (2018) (40), in pain-free overweight individuals, only observed augmented pressure pain threshold over the exercised muscles after 6 weeks of moderate-intensity continuous cycling training and not after volume-matched high intensity training.

It is important to mention that none of the above studies tried to establish mechanisms underneath training-induced analgesic effects. Some reports indicate that exercise training decreases cardiovascular sympathetic modulation mainly via central command (41). However, it has also been proposed that training modulates the exercise pressor reflex at cardiovascular level by attenuating the peripheric discharge of group III and IV muscle afferents in response to noxious, metabolic and mechanical stimuli, and thus regulating the sensation of nociception. Sinoway et al. (1996) (42) reported that 4 weeks of forearm training reduce sympathetic responses and mean arterial pressure during rhythmic voluntary handgrip. In addition, there is compelling evidence that endurance-trained individuals have a lower exercise pressor response compared to untrained people (43, 44). Thus, the available data indicate some level of adaptation within the exercise pressor reflex gain following low-resistance high-repetition muscle training, and this is in accordance with

the findings of Somers et al. (1992) (45).

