2.2 Aim #2

2.2.1 Participants

The intervention study will enroll 24 participants ((G Power 3.0.10 software) to achieve 80% of correctly rejecting the null hypothesis, based on Jones et al., (2016) (11)). Eight participants will be randomly allocated to each exercise modality (i.e. resistance, supramaximal and endurance). Specific inclusion and exclusion criteria are discussed in subsection 2.4.1.

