2.3 Aim #3

2.3.1 Participants

We will recruit a total of 30 participants. Sample size is overestimated in order to allow us to accommodate an attrition rate of ~ 20% during follow up, once participants will only be eligible for final testing if they attain at least 85% of the training sessions, with the goal of allocating at least 8 participants to each of the three training groups (G Power 3.0.10 software; to achieve 80% of correctly reject the null hypothesis, based on Jones et al. 2014 (38)). Specific inclusion and exclusion criteria are discussed in

subsection 2.4.1

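### Aim #2 compares modalities on change scores; ANCOVA on the pre value already collected would usually be more precise, by an amount that depends on the pre-post correlation and SDs

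*Combined protocol and SAP*

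**What the plan says.** **Design of Aim #2.** Section 2.2.1 plans 24 participants: "Eight participants will be randomly allocated to each exercise modality". Modality is therefore a randomised, between-participant factor. Section 2.2.2 adds a crossover with rest: "on 2 different days, participants will be tested before and after performing acute bouts of different exercise modalities or" passive rest. A pre value is thus collected on each test day.

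**Analysis.** For Aim #2, section 2.4.13 plans a repeated measures ANOVA with time (pre, post), "condition (resistance vs. supramaximal vs. endurance exercise) and time-by-condition interactions on pain tolerance/threshold/ratings" and further outcomes. It names no baseline covariate. The significance level is 0.05.

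**Hypothesis.** Section 1.3 expects resistance and supramaximal exercise to raise nociceptive tolerance more than endurance exercise does. The interaction is the term that addresses this. The condition main effect averages pre and post, so it does not.

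**Sample size.** Section 2.2.1 says the number was chosen "to achieve 80% of correctly rejecting the null hypothesis", with one cited study as its source. Section 2.3.1 (Aim #3) aims for "at least 8 participants to each of the three training groups (G Power 3.0.10 software; to achieve 80% of correctly reject the null hypothesis" and cites a different study. Neither section gives an outcome, effect size, SD, correlation or test.

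**The concern.** With 8 participants per modality, the intervals for modality differences will be wide, so precision that costs nothing is worth having. The change score subtracts the whole pre value from the post value, whatever the correlation between them. When that correlation is moderate, this adds noise that ANCOVA would avoid by estimating the slope. Because allocation is random, both methods estimate the same modality difference, so the choice turns on precision.

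What is at stake is the width of the intervals and the power for the section 1.3 modality hypothesis. The validity of the result is not in question. A smaller matter is that a reader cannot tell which comparison the 80% refers to, which makes a non-significant modality difference harder to interpret.

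**Working it through.** **The plan's own figure.** N = 24 at 80% power cannot be reproduced, because the effect, SD, correlation, outcome and test are not given. The check below starts instead from a difference at which the planned interaction test has 80% power.

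**Inputs from the documents.** Three groups of 8 (2.2.1); two time points and alpha 0.05 (2.4.13). **Assumed:** the pre-post correlation r, the ratio k of post SD to pre SD, normal outcomes and one modality differing from the other two.

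**1. Difference needed by the planned test.** The time-by-condition F is a one-way ANOVA on post minus pre, with 2 and 21 df. For 80% power the noncentrality must be 11.15. With one modality differing by δ (in SDs of change), noncentrality = 8 × (2/3) × δ². So δ = √(11.15 × 3/16) = 1.45.

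**2. Variance per observation, equal SDs (pre SD = 1).**
- Change score: 2(1 − r)
- ANCOVA: (1 − r²) × [1 + 1/(24 − 3 − 2)] = (1 − r²) × 20/19
- Ratio, ANCOVA to change score: ((1 + r)/2) × 20/19

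The ratio equals 1 at r = 2 × 19/20 − 1 = 0.90, or about 0.89 once the lost error df (20 against 21) is counted.

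**3. Power of ANCOVA at the difference where the change score has 80% (simulation, equal SDs).**

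| r | Variance ratio | ANCOVA power |
|---|---|---|
| 0.5 | 0.79 | about 89% |
| 0.7 | 0.89 | about 84% |
| 0.8 | 0.95 | about 82% |
| 0.9 | 1.00 | about 80% |
| 0.95 | 1.03 | about 79% |

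Type I error was 0.049 to 0.052 for both methods. For resistance and supramaximal pooled against endurance, the mean 95% CI half-width in raw SDs goes from 0.89 to 0.79, 0.69 to 0.65, 0.56 to 0.55, and 0.40 to 0.40 at r = 0.5, 0.7, 0.8 and 0.9.

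**4. Unequal SDs.** The change-score variance becomes 1 + k² − 2rk, and the ANCOVA variance k²(1 − r²) × 20/19.
- k = 1.2, r = 0.8: 1.44 × 0.36 × 20/19 = 0.546 against 2.44 − 1.92 = 0.52, a ratio of 1.05. ANCOVA power is about 83 / 79 / 78 / 79 / 83% at r = 0.5 / 0.7 / 0.8 / 0.9 / 0.95.
- k = 0.8: ratios run from 0.55 to 0.67 over r 0.5 to 0.95, and ANCOVA power is about 93 to 97%.
- k = 1.1: ANCOVA is the less precise method for r between about 0.76 and 0.97.

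**5. Detectable difference under ANCOVA (20 error df, equal SDs, one modality differing).** The noncentrality needed is 11.24, so δ ≈ 1.446 × √[((1 + r)/2) × (20/19) × (11.24/11.15)] = 1.29 / 1.37 / 1.41 / 1.45 SDs of change at r = 0.5 / 0.7 / 0.8 / 0.9.

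**6. What the cited studies compared, as section 1.1 describes them.** The Aim #2 source took measurements "after elbow flexion isometric exercise at 40% MVC for 3 min", and its effect on laser-evoked potentials "was not statistical different from the passive rest control condition". The Aim #3 source found "increases in ischemic pain tolerance in non-exercising region (upper limb), but not in pain threshold, after cycling training". Neither description is of a comparison between modalities. That leaves open which comparison the 80% covers; it does not show which calculation was run.

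**The case against.** **The planned test is valid and the gain may be small.** This stands. Pre and post are measured in the same session, and pressure pain threshold is the average of three readings (2.4.8), so a high r is plausible, although the documents give no value. At r = 0.8 the gain is 2 points of power, and at 0.9 there is none.

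**The 0.9 threshold is conditional.** This also stands. A reader might infer that ANCOVA wins at every r below 0.9, but that needs equal pre and post SDs. If the post SD is larger, ANCOVA can lose slightly within that range. The loss is at most about 5% of variance, while the possible gains are much larger.

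**The covariate is measured after allocation.** Under 2.2.2, endurance and resistance participants attend an earlier testing visit; none is stated for supramaximal. The pre values could therefore differ by modality for a reason other than chance. The instruction to avoid strenuous activity for 24 hours (2.4.1) limits this, and change scores are not immune to it either. It is a caveat and does not defeat the change.

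**The rest day is a more direct gap.** The passive-rest day does not appear in the Aim #2 model of 2.4.13. The ANCOVA proposed here does not use it either, so exercise against rest has to be specified separately.

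**The 80% may be sound.** A reader might infer that 24 is too few or that the 80% is wrong. The documents do not support that. With 24 participants, 80% power fits a paired comparison at a standardised difference of about 0.60. It also fits a within-between interaction at f about 0.34 (r = 0.5) or 0.26 (r = 0.7). Which was meant is unstated.

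**Conclusion.** The point holds as a cheap improvement. The Aim #2 modality comparison is a valid change-score test, and ANCOVA on the pre value is more precise if pre and post SDs are about equal and r is below about 0.9. The size ranges from about 9 points of power at r = 0.5 to none at 0.9 and a loss of about 1 point at 0.95. With a post SD 20% larger the range shifts to a loss of 1 to 2 points at r 0.7 to 0.9; with it 20% smaller, to a gain of about 13 to 17 points. These figures assume 8 per group, normal outcomes and random baselines. Since r and the SDs are unknown, no single gain can be claimed.

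The sample-size remark is about disclosure only. The outcome and comparison behind the 80% are unstated, and no error is shown.

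**What to change.** **In 2.4.13, Aim #2, add:** 'For outcomes summarised as one pre and one post value, modalities will be compared by ANCOVA of the exercise-day post value on modality, with the exercise-day pre value as covariate; modality differences will be reported with two-sided 95% CIs.' Keep the time effect as planned, and state a separate comparison for exercise against passive rest.

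**In Aim #3,** use the same approach only if allocation to training groups is random, which 2.3.1 and 2.3.2 do not state. Do not use it for exercise performance, which is a different test in each group (2.3.4.1 to 2.3.4.3).

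**In 2.2.1 and 2.3.1,** name the outcome and comparison that the 80% covers. Any detectable difference added must match the test used. For ANCOVA in Aim #2, that is the r-dependent set in step 5 of the working, with equal SDs stated. The 1.45 SD figure on 21 df belongs only to the change-score test. A pairwise figure should say that it is unadjusted for multiplicity.

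**Cost.** Wording only, with no extra participants or measurements. ANCOVA uses one error degree of freedom and may give up about 1 to 2 points of power if r is above 0.9 or the post SD is larger than the pre SD.
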